5.3.5.5 Abnormal Vital Sign Values

Not every vital sign abnormality qualifies as an adverse event. A vital sign result must be reported as an adverse event if it meets any of the following criteria:

- Is accompanied by clinical symptoms

- Results in a change in study treatment (e.g., dosage modification, treatment interruption, or treatment discontinuation)
- Results in a medical intervention or a change in concomitant therapy
- Is clinically significant in the investigator's judgment

It is the investigator's responsibility to review all vital sign findings. Medical and scientific judgment should be exercised in deciding whether an isolated vital sign abnormality should be classified as an adverse event.

If a clinically significant vital sign abnormality is a sign of a disease or syndrome (e.g., high blood pressure), only the diagnosis (i.e., hypertension) should be recorded on the Adverse Event eCRF.

Observations of the same clinically significant vital sign abnormality from visit to visit should only be recorded once on the Adverse Event eCRF (see Section 5.3.5.4 for details on recording persistent adverse events).

5.3.5.6 Abnormal Liver Function Tests

The finding of an elevated ALT or AST ($>3 \times$ baseline value) in combination with either an elevated total bilirubin ($>2 \times$ ULN) or clinical jaundice in the absence of cholestasis or other causes of hyperbilirubinemia is considered to be an indicator of severe liver injury (as defined by Hy's law). Therefore, investigators must report as an adverse event the occurrence of either of the following:

- Treatment-emergent ALT or AST $>3 \times$ baseline value in combination with total bilirubin $>2 \times$ ULN (of which $\geq 35\%$ is direct bilirubin)
- Treatment-emergent ALT or AST $>3 \times$ baseline value in combination with clinical jaundice

The most appropriate diagnosis or (if a diagnosis cannot be established) the abnormal laboratory values should be recorded on the Adverse Event eCRF (see Section 5.3.5.1) and reported to the Sponsor immediately (i.e., no more than 24 hours after learning of the event), either as a serious adverse event or a non-serious adverse event of special interest (see Section 5.4.2).

5.3.5.7 Deaths

All deaths that occur during the protocol-specified adverse event reporting period (see Section 5.3.1), regardless of relationship to study drug, must be recorded on the Adverse Event eCRF and immediately reported to the Sponsor (see Section 5.4.2). This includes death attributed to progression of malignant breast cancer.

Death should be considered an outcome and not a distinct event. The event or condition that caused or contributed to the fatal outcome should be recorded as the single medical concept on the Adverse Event eCRF. Generally, only one such event should be reported. If the cause of death is unknown and cannot be ascertained at the time of

reporting, "unexplained death" should be recorded on the Adverse Event eCRF. If the cause of death later becomes available (e.g., after autopsy), "unexplained death" should be replaced by the established cause of death. *The term "sudden death" should not be used unless combined with the presumed cause of death (e.g., "sudden cardiac death").*

If the death is attributed to progression of malignant breast cancer, "malignant disease progression" should be recorded on the Adverse Event eCRF.

Deaths that occur after the adverse event reporting period should be reported as described in Section 5.6.

5.3.5.8 Preexisting Medical Conditions

A preexisting medical condition is one that is present at the screening visit for this study. Such conditions should be recorded on the General Medical History and Baseline Conditions eCRF.

A preexisting medical condition should be recorded as an adverse event only if the frequency, severity, or character of the condition worsens during the study. When recording such events on the Adverse Event eCRF, it is important to convey the concept that the preexisting condition has changed by including applicable descriptors (e.g., "more frequent headaches").

5.3.5.9 Lack of Efficacy or Worsening of Breast Cancer

Events that are clearly consistent with the expected pattern of progression of the underlying disease should not be recorded as adverse events. These data will be captured as efficacy assessment data only. In most cases, the expected pattern of progression will be based on modified RECIST v1.1. In rare cases, the determination of clinical progression will be based on symptomatic deterioration. However, every effort should be made to document progression through use of objective criteria. If there is any uncertainty as to whether an event is due to disease progression, it should be reported as an adverse event.

5.3.5.10 Hospitalization or Prolonged Hospitalization

Any adverse event that results in hospitalization (i.e., in-patient admission to a hospital) or prolonged hospitalization should be documented and reported as a serious adverse event (per the definition of serious adverse event in Section 5.2.2), except as outlined below.

An event that leads to hospitalization under the following circumstances should not be reported as an adverse event or a serious adverse event:

- Hospitalization for respite care

- Hospitalization for a preexisting condition, provided that all of the following criteria are met:
 - The hospitalization was planned prior to the study or was scheduled during the study when elective surgery became necessary because of the expected normal progression of the disease
 - The patient has not experienced an adverse event
- Hospitalization due solely to progression of the underlying cancer
- Hospitalization for outpatient care outside of normal clinical operating hours that is required per protocol or per local standard of care

The following hospitalization scenarios are not considered to be serious adverse events, but should be reported as adverse events instead:

- Hospitalization for an adverse event that would ordinarily have been treated in an outpatient setting had an outpatient clinic been available

An event that leads to hospitalization under the following circumstances is not considered to be a serious adverse event, but should be reported as an adverse event instead:

- *Hospitalization that was necessary because of patient requirement for outpatient care outside of normal outpatient clinic operating hours*

5.3.5.11 Adverse Events Associated with an Overdose or Error in Drug Administration

An overdose is the accidental or intentional use of a drug in an amount higher than the dose being studied. An overdose or incorrect administration of study treatment is not itself an adverse event, but it may result in an adverse event. All adverse events associated with an overdose or incorrect administration of study drug should be recorded on the Adverse Event eCRF. If the associated adverse event fulfills seriousness criteria, the event should be reported to the Sponsor immediately (i.e., no more than 24 hours after learning of the event; see Section 5.4.2).

No safety data related to overdosing of GDC-0810 are available.

5.3.5.12 Adverse Events that Change Grade over Time

When a patient experiences an adverse event that later increases in grade, the increased grade should be recorded on the Adverse Event eCRF. In general, subsequent adverse-event grade decreases (with the exception of resolution) should not be recorded on the Adverse Event eCRF, as maximum grade is of primary interest for safety reporting. However, any additional upgrades and downgrades of diarrhea outside of the initial and maximum grade should be recorded on the Adverse Event Grade Changes eCRF to more fully assess the impact of time and/or supportive care on diarrhea symptoms.

5.3.5.13 Patient-Reported Outcome Data

Adverse-event reports will not be derived from PRO data by the Sponsor, and safety analyses will not be performed using PRO data. The methods for collecting and analyzing PRO data are different from those for the ascertainment of observed or volunteered adverse events. Because of these differences, PRO data will not be reported as adverse events, and no attempt will be made to resolve any noticeable discrepancies between PRO data and observed or volunteered adverse events. The PRO data will be presented in separate tables, figures, and data listings from the adverse-event data, and will be included in the appropriate section of the final study report.

5.4 IMMEDIATE REPORTING REQUIREMENTS FROM INVESTIGATOR TO SPONSOR

Certain events require immediate reporting to allow the Sponsor to take appropriate measures to address potential new risks in a clinical trial. The investigator must report such events to the Sponsor immediately; under no circumstances should reporting take place more than 24 hours after the investigator learns of the event. The following is a list of events that the investigator must report to the Sponsor within 24 hours after learning of the event, regardless of relationship to study drug:

- Serious adverse events (see Section 5.4.2 for further details)
- Non-serious adverse events of special interest (see Section 5.4.2 for further details)
- Pregnancies (see Section 5.4.3 for further details)

The investigator must report new significant follow-up information for these events to the Sponsor immediately (i.e., no more than 24 hours after becoming aware of the information). New significant information includes the following:

- New signs or symptoms or a change in the diagnosis
- Significant new diagnostic test results
- Change in causality based on new information
- Change in the event's outcome, including recovery
- Additional narrative information on the clinical course of the event

Investigators must also comply with local requirements for reporting serious adverse events to the local health authority and Institutional Review Board (IRB)/Ethics Committee (EC).

5.4.2.2 Events That Occur after Study Drug Initiation

After initiation of study drug, serious adverse events and non-serious adverse events of special interest will be reported until 28 days after the last dose of study drug. Investigators should record all case details that can be gathered immediately (i.e., within 24 hours after learning of the event) on the Adverse Event eCRF and submit the report via the electronic data capture (EDC) system. A report will be generated and sent to Safety Risk Management by the EDC system.

In the event that the EDC system is unavailable, the Serious Adverse Event/Adverse Event of Special Interest Reporting Form provided to investigators should be completed and submitted to the Sponsor or its designee immediately (i.e., no more than 24 hours after learning of the event), by faxing the form using the fax number or email address provided above in Section 5.4.2.1. Once the EDC system is available, all information will need to be entered and submitted via the EDC system.

Instructions for reporting post-study adverse events are provided in Section 5.6.

5.4.3 Reporting Requirements for Pregnancies

5.4.3.1 Pregnancies in Female Patients

Patients will be instructed to immediately inform the investigator if they become pregnant during the study or within 28 days after the last dose of study drug *or 1 year after the last dose of fulvestrant*. A Pregnancy Report eCRF should be completed by the investigator immediately (i.e., no more than 24 hours after learning of the pregnancy) and submitted via the EDC system. A pregnancy report will automatically be generated and sent to Safety Risk Management. Pregnancy should not be recorded on the Adverse Event eCRF. The investigator should discontinue study drug and counsel the patient, discussing the risks of the pregnancy and the possible effects on the fetus. Monitoring of the patient should continue until conclusion of the pregnancy. Any serious adverse events associated with the pregnancy (e.g., an event in the fetus, an event in the mother during or after the pregnancy, or a congenital anomaly/birth defect in the child) should be reported on the Adverse Event eCRF.

In the event that the EDC system is unavailable, the Clinical Trial Pregnancy Reporting Form provided to investigators should be completed and submitted to the Sponsor or its designee immediately (i.e., no more than 24 hours after learning of the pregnancy), by faxing the form using the fax number or email address provided to investigators. Once the EDC system is available, all information will need to be entered and submitted via the EDC system.

5.4.3.2 Congenital Anomalies/Birth Defects and Abortions

Any congenital anomaly/birth defect in a child born to a female patient exposed to study drug should be classified as a serious adverse event, recorded on the Adverse Event eCRF, and reported to the Sponsor immediately (i.e., no more than 24 hours after learning of the event; see Section 5.4.2). Any abortion should be reported in the same fashion (as the Sponsor considers abortions to be medically significant).

5.5 FOLLOW-UP OF PATIENTS AFTER ADVERSE EVENTS

5.5.1 Investigator Follow-Up

The investigator should follow each adverse event until the event has resolved to baseline grade or better, the event is assessed as stable by the investigator, the patient is lost to follow-up, or the patient withdraws consent. Every effort should be made to follow all

serious adverse events considered to be related to study drug or trial-related procedures until a final outcome can be reported.

During the study period, resolution of adverse events (with dates) should be documented on the Adverse Event eCRF and in the patient's medical record to facilitate source data verification.

All pregnancies reported during the study should be followed until pregnancy outcome. If the EDC system is not available at the time of pregnancy outcome, follow reporting instructions provided in Section [5.4.3.1](#).

5.5.2 Sponsor Follow-Up

For serious adverse events, non-serious adverse events of special interest, and pregnancies, the Sponsor or a designee may follow up by telephone, fax, electronic mail, and/or a monitoring visit to obtain additional case details and outcome information (e.g., from hospital discharge summaries, consultant reports, autopsy reports) in order to perform an independent medical assessment of the reported case.

5.6 POST-STUDY ADVERSE EVENTS

The Sponsor should be notified if the investigator becomes aware of any serious adverse event that occurs after the end of the adverse event reporting period (defined as 28 days after the last dose of study drug), if the event is believed to be related to prior study drug treatment.

The investigator should report these events directly to the Sponsor or its designee, either by faxing or by scanning and emailing the Serious Adverse Event/Adverse Event of Special Interest Reporting Form using the fax number or email address provided to investigators.

5.7 EXPEDITED REPORTING TO HEALTH AUTHORITIES, INVESTIGATORS, INSTITUTIONAL REVIEW BOARDS, AND ETHICS COMMITTEES

The Sponsor will promptly evaluate all serious adverse events and non-serious adverse events of special interest against cumulative product experience to identify and expeditiously communicate possible new safety findings to investigators, IRBs, ECs, and applicable health authorities based on applicable legislation.

To determine reporting requirements for single adverse event cases, the Sponsor will assess the expectedness of these events using the following reference documents:

- GDC-0810 Investigator's Brochure
- SmPC for fulvestrant

The Sponsor will compare the severity of each event and the cumulative event frequency reported for the study with the severity and frequency reported in the applicable reference document.

Reporting requirements will also be based on the investigator's assessment of causality and seriousness, with allowance for upgrading by the Sponsor as needed.

6. STATISTICAL CONSIDERATIONS AND ANALYSIS PLAN

Primary and secondary efficacy analyses will include all randomized patients, with patients allocated to the randomized treatment arm. In addition to the all-randomized patient population (the ITT population), analysis of PFS, ORR, and CBR will be repeated in the patient subsets defined by their *ESR1* mutation status.

Safety analyses will include all patients who received at least one dose of the study treatment, with patients allocated to the treatment arm associated with the regimen actually received.

There will be no adjustments made for multiple comparisons when analyzing the primary and secondary endpoints.

6.1 DETERMINATION OF SAMPLE SIZE

The trial is designed to evaluate the clinical activity and safety of GDC-0810 compared with fulvestrant in patients with ER-positive locally advanced or MBC. It is for hypothesis generation, and is not powered to detect minimum clinically meaningful difference between treatment arms.

A total of approximately 152 patients will be enrolled in this study. It is assumed that the median duration of PFS in the fulvestrant control arm is 5.5 months and 8.5 months in the GDC-0810 arm. The final analysis of all randomized patients will be triggered by the occurrence of approximately 95 PFS events, which is expected to occur 26 months after the first patient is randomized. [Table 4](#) shows expected probabilities of observing a hazard ratio of less than 0.5, 0.6 and 0.7 in the final analysis in all randomized patients under varying assumptions for the true underlying hazard ratio. Note that formal hypothesis testing is limited. Rather than testing treatment differences at a statistically significant type I error level of 5%, 90% confidence intervals (CI) for the hazard ratio will be calculated.

At a target hazard ratio of 0.6, the corresponding 90% CI based on 95 PFS events is (0.43, 0.84) which is considered to provide meaningful precision.

Table 4 Expected Probability of Observing a Hazard Ratio of <0.5, <0.6, or <0.7 in the Final Analysis (All Patients)

True HR	95 PFS Events in ITT Population		
	Observed HR < 0.50	Observed HR < 0.60	Observed HR < 0.70
0.4	0.86	0.98	0.99
0.5	0.50	0.81	0.95
0.6	0.19	0.50	0.77
0.7	0.05	0.23	0.50
0.8	0.01	0.08	0.26

HR=hazard ratio; ITT=intent to treat; PFS=progression-free survival.

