4.2 METHOD OF TREATMENT ASSIGNMENT

After written informed consent has been obtained and eligibility has been established and approved, the study site will obtain the patient's identification number and treatment assignment from the Interactive Web Response System (IWRS). Patients will be randomized to receive either GDC-0810 or fulvestrant in an approximate 1:1 ratio through the use of a permuted block randomization method.

Randomization will be stratified by the following criteria:

- Visceral versus non-visceral disease:
 - Visceral disease: metastatic disease in the lung, liver, adrenal glands, brain, heart, pericardium, pleura, peritoneum, or other organs of the chest, abdomen and pelvis
 - Non-visceral disease: absence of metastatic disease in visceral organs. Pleural effusions and/or ascites. Disease involving lymph nodes and disease involving bone are not considered to be visceral disease.

- Geographical region:
 - United States
 - European Union
 - Rest of World (remaining countries)

The Sponsor, the investigators, and the patients will be unblinded to treatment assignment.

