6.4.1 Primary Efficacy Endpoint

The primary efficacy endpoint is PFS, defined as the time from randomization to the first occurrence of disease progression, as determined by investigator review of tumor assessments using RECIST v1.1 or death on study from any cause. The primary efficacy analyses will be performed on all randomized patients as well as on patients with *ESR1* LBD mutations detected in circulating cell-free DNA, with patients allocated to the treatment arm assigned at randomization.

For patients without disease progression or death as of the clinical data cutoff date, their PFS will be censored at the time of last tumor assessment (or censored at the date of randomization, if no tumor assessment was performed after the baseline visit). For patients who start other anti-cancer treatment prior to the documented PFS event, the primary PFS analysis will include PFS events after other anti-cancer treatment. PFS

sensitivity analysis will be performed, censoring PFS on the last tumor assessment prior to starting other anti-cancer therapy.

The two-sided log-rank test stratified by the stratification factors will be used as the primary analysis. The Kaplan-Meier approach will be used to estimate median PFS for each treatment arm. Cox proportional hazards models stratified by the stratification factors will be used to estimate a hazard ratio and its 90% CI. The results from the unstratified analysis will also be provided.

Exploratory analysis for PFS may be performed on patient subgroups by demographic disease characteristics.

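### Does the target hazard ratio of 0.6 conflict with the assumed median PFS of 5.5 and 8.5 months?

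*Combined protocol and SAP*

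**What the plan says.** Section 6.1 (Determination of Sample Size) gives its planning figures in this order:

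- Size: "A total of approximately 152 patients will be enrolled in this study".
- Effect in months: "It is assumed that the median duration of PFS in the fulvestrant control arm is 5.5 months and 8.5 months in the GDC-0810 arm".
- Trigger: "The final analysis of all randomized patients will be triggered by the occurrence of approximately 95 PFS events", expected 26 months after the first patient is randomized.
- Table 4: chances of observing an HR below 0.5, 0.6 and 0.7 at 95 events, for true HRs of 0.4, 0.5, 0.6, 0.7 and 0.8.
- Precision: "At a target hazard ratio of 0.6, the corresponding 90% CI based on 95 PFS events is (0.43, 0.84"), which the section judges to be useful precision.

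The synopsis repeats the medians and the precision statement. Neither place names a distribution for PFS, states the HR that the medians imply, or says where the target of 0.6 comes from. Section 6.1 also says of the trial: "It is for hypothesis generation, and is not powered to detect minimum clinically meaningful difference between treatment arms". Section 6.9 and Table 5 give the same kind of probabilities at 62 events.

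**The concern.** The ratio of medians is the usual quick route to an HR, and 5.5/8.5 is about 0.65. A reader who takes the medians as the planning effect then meets a CI and a table row for a stronger effect. This could mean that the precision was worked out for a more favourable drug than the one assumed, or that the number of events was set from one effect and described with another. If a go/no-go rule or a power claim rested on 0.6, the trial would be less likely to succeed under its own medians than the text suggests.

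**Working it through.** **Inputs.** Medians 5.5 and 8.5 months, 152 patients, 95 events, target HR 0.6 and analysis at 26 months (Section 6.1). Interim at 62 events (Section 6.9). Enrollment over about 22 months (synopsis, Length of Study). Allocation "in an approximate 1:1 ratio through the use of a permuted block randomization method" (Section 4.2). With equal arms and d events, SE(log HR) = 2/√d.

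**1. The plan's own CI.** 90% CI = HR × exp(±1.645 × 2/√95) = HR × exp(±0.3375). At 0.6 this is 0.428 to 0.841, which is the printed 0.43 to 0.84.

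**2. The plan's own tables.** P(observed HR < c) = Φ(ln(c/HR) × √d/2). All 30 cells of Tables 4 and 5 reproduce to within 0.007.

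**3. HR implied by the medians, if PFS is exponential.** 5.5/8.5 = 0.647. If the medians are rounded to 0.1 month, the range is 5.45/8.55 = 0.637 to 5.55/8.45 = 0.657. Rounding of the medians therefore does not reach 0.6.

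**4. What moves at 0.647.**

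| | HR 0.6 | HR 0.647 |
|---|---|---|
| 90% CI, 95 events | 0.43 to 0.84 | 0.46 to 0.91 |
| Upper/lower limit | 1.96 | 1.96 |
| P(obs < 0.5 / 0.6 / 0.7), 95 events | 0.19 / 0.50 / 0.77 | 0.10 / 0.36 / 0.65 |
| P(obs < 0.5 / 0.6 / 0.7), 62 events | 0.24 / 0.50 / 0.73 | 0.16 / 0.38 / 0.62 |

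The ratio of the limits is exp(2 × 0.3375) = 1.96 whatever the HR. The interval shifts towards 1 but is no wider on the log scale, and its upper limit stays below 1.

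**5. Does the plan cover 0.647?** With a control median of 5.5 months and exponential PFS, the 0.6 row corresponds to a GDC-0810 median of 5.5/0.6 = 9.2 months and the 0.7 row to 5.5/0.7 = 7.9 months. These lie on either side of 8.5.

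**6. Must the medians and 0.6 disagree?** No. Under Weibull PFS with proportional hazards, HR = (5.5/8.5)^k. Setting this to 0.6 gives k = ln(0.6)/ln(0.647) = 1.17, a mildly rising hazard. The range is 1.13 to 1.22 over the rounding range of the medians.

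**7. Does the choice affect the projected timing?** Assume uniform accrual over 22 months, exponential PFS, no dropout and 76 patients per arm. Expected events per arm at 26 months are 76 × [1 − (e^(−4λ) − e^(−26λ))/(22λ)], with λ = ln 2/median. The control arm gives 60.5. The GDC-0810 arm gives 50.5 at a median of 8.5 months and 48.6 at 9.17 months. The totals are 111 and 109, about two events apart. The level depends on the assumed accrual pattern and dropout, but the analysis is triggered by events and not by the calendar.

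**The case for a change.** The best argument for a change is that 0.6 looks like the figure behind the event count. By Schoenfeld's formula, 80% power at two-sided 10% with HR 0.6 needs 4 × (1.645 + 0.842)²/(ln 0.6)² = 94.8 events, which rounds up to 95. At 0.647 the same 95 events give about 68% power, and 131 would be needed for 80%. Nor can the target be read as 0.647 rounded to one decimal, because the printed CI is the one at exactly 0.600. The medians are the only effect stated in months, so a clinical reader will naturally start from them.

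Part of this stands. The plan leaves the link unstated, and a reader who wants the row for 0.647 has to derive that HR and interpolate. The power argument does not carry further. The plan claims no power and says that the trial is not powered for a minimum clinically meaningful difference, so there is no stated figure for 68% to contradict. The match with 95 is suggestive of how the number was chosen, but does not prove it. The text also never says that 0.6 was derived from the medians. The medians come just before the event trigger and its timing, while the target stands in a separate paragraph as the point at which precision is illustrated. A target and a planning projection may differ.

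**Conclusion.** No change to the plan follows. This is a missing explanation, not an error or a contradiction. The mismatch appears only once exponential PFS is added, which the documents do not state. Under that assumption it is 0.647 against 0.6: the illustrative 90% CI moves from 0.43–0.84 to 0.46–0.91 with the same relative width, and the chance of observing an HR below 0.6 falls from 0.50 to 0.36. These figures also rest on equal allocation and the usual large-sample SE of 2/√d.

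Neither the target nor the medians enter the analysis. Section 6.4.1 says: "The two-sided log-rank test stratified by the stratification factors will be used as the primary analysis", with the HR and its 90% CI estimated from the data by a stratified Cox model. No stopping or go/no-go rule refers to 0.6, and Tables 4 and 5 already show how the trial behaves over true HRs from 0.4 to 0.8. Enrollment has been discontinued (Section 3.1), and Section 2 says that the primary objectives will not be met. Following the plan as written gives the same results and conclusions with or without a sentence joining the two figures.
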